A SINGLE BLIND, PROSPECTIVE, RANDOMIZED CONTROLLED TRIAL ON THE EFFECT OF LOCAL STEROID APPLICATION VERSUS INTRAVENOUS STEROIDS ON DYSPHAGIA FOLLOWING ANTERIOR CERVICAL DISECTION AND FUSION

PRINCIPAL INVESTIGATOR: [name], FACS
[name]
[name]
[contact]
[contact]
[contact]

SUB-INVESTIGATORS: [name]
Northwestern University

[name]
Northwestern University

[name], MD
University of Wisconsin-Madison

[name], MD
OrthoCarolina Research Institute

PARTICIPATING SITES: Northwestern Memorial Faculty Foundation
(NMFF)
[name]
[name]
[contact]

Northwestern University (NU)
[name]
[name]

OrthoCarolina Research Institute
[name]
[name]

University of Wisconsin-Madison

FUNDING AGENCY: Cervical Spine Research Society (CSRS)

Synopsis

Title	A single blind, prospective, randomized controlled trial on the effect of local steroid application versus intravenous steroids on dysphagia following anterior cervical discectomy and fusion (ACDF)
Short Title	Effect of local application vs. IV steroids on dysphagia after ACDF
Protocol Date	12/14/2015
Study Duration	2 years
Study Center(s)	Northwestern Memorial Faculty Foundation (NMFF), Northwestern University (NU), University of Wisconsin-Madison, OrthoCarolina Research Institute
Objectives	Local application of steroids in ACDF surgery will lead to decreased incidence of dysphagia compared to intravenous steroids or a control group
Number of Subjects	85 (randomized to group I (control group), group II (10 mg of intraoperative intravenous decadron), or group III (40mg of triamcinolone placed on cervical plate), i.e. 25 per group.
Diagnosis and Main Inclusion Criteria	Patients undergoing ACDF (single or multi-level) for the treatment of radiculopathy or myelopathy by Drs. [name], [name], and [name].

TABLE OF CONTENTS

Synopsis	2
1.0 Introduction	4
2.0 Study Objectives	4,5
3.0 Selection of Subjects	5
3.1 Inclusion Criteria.....	5
3.2 Exclusion Criteria.....	5
4.0 Subject Registration	5
5.0 Study Design & Methods	5,6
6.0 Statistical Plan	6
7.0 Data Collection & Record Keeping	6
8.0 References	7
Appendices	8

1.0 INTRODUCTION - BACKGROUND AND RATIONALE

Dysphagia is a common complication after ACDF.¹ PSTS is also a natural sequela of ACDF and can lead to airway compromise among other complications.² Previous studies have demonstrated that administration of intravenous methylprednisolone (1mg/kg) after anterior cervical spine surgery reduced the incidence of pharyngolaryngeal lesions as identified by nasofibrosopic examination.³ Lee et al. prospectively evaluated 50 patients and determined that local application of steroids in the retropharyngeal area following ACDF reduced PSTS and odynophagia as measured by the Visual Analogue Scale (VAS) and the Neck Disability Index (NDI) compared to a control group.⁴ Furthermore, there were no adverse events/reactions from local application of steroid on a gel foam sponge in the setting of anterior spinal surgery. There are no studies in the current literature that investigate the incidence of dysphagia with application of local steroids after ACDF, nor are there any studies that stratify the efficacy of local steroids compared to intravenous steroids. There is also no current spine literature that directly compares the efficacy of intravenous steroids versus local steroids in the incidence of dysphagia or dysphonia. Our study will be the first in the literature to assess the efficacy of local steroids in reducing the incidence of dysphagia after anterior cervical spine surgery, and as a result, may improve patient outcomes after ACDF.

Dysphagia and dysphonia are common complications after anterior cervical spine surgery.¹ Despite their clinical importance, studies on the treatment and/or prevention of these complications are limited due to the lack of valid and reliable outcome measures. The majority of research is found in the otolaryngology literature and has focused on disease pathophysiology, diagnosis, and therapy.

2.0 OBJECTIVES

- To determine if the use of steroids decreases the incidence of dysphasia after anterior cervical discectomy and fusion (ACDF).
- If steroids are useful, determine which method of steroid administration is most efficacious (IV versus local application).
- We hypothesize that local application of steroids in ACDF surgery will lead to a decreased incidence of dysphagia, in the postoperative period as compared to intravenous steroids or a control group.
- To evaluate the incidence of dysphonia, as measured by the Voice Handicap Index (VHI-10), as well as other validated outcome measures (NDI, VAS, EQ-5D).

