5.0 STUDY DESIGN & METHODS

We intend to prospectively evaluate 85 patients as part of a single blind, randomized controlled study. Subjects would be randomized to group I (control group, no steroid), group II (10 mg of intraoperative intravenous decadron with gel foam sponge placed on cervical plate), or group III (40mg of triamcinolone on gel foam sponge dabbed on the anterior cervical plate). Subjects will be blinded to the treatment arm. Randomization will take place on the day of surgery. 85 envelopes will be sealed, 25 of which will contain a document specifying “control”, “iv steroids”, or “steroid sponge”. The 75 envelopes will then be shuffled to create a random assortment. The circulating nurse in the OR will at random choose one envelop prior to the start of the operative procedure. This will in turn specify the treatment group for each patient.

There is no standard of care regarding the use of IV or local steroids in the setting of ACDF. Currently, the use of either IV or local steroids is at the discretion of the attending surgeon. To my knowledge, there are several spine surgeons at our institution that currently use no steroid, and others who use a combination of IV and/or local steroids.

The primary outcome measure is the incidence of dysphagia as measured by Eating Assessment Tool (EAT-10) and the Bazaz score. The patients will prospectively fill out these surveys preoperatively, post-operative day 1, week 2, week 6, month 3, month 6, and 1 year as a measure of dysphagia. The standard of care is to see patients in the office at 2 weeks, 6 weeks, 3 months, 6 months, and 1 year after surgery, and therefore, no extra visits will be necessary for this study. X-rays will be taken at 6 weeks, 3

months, and 12 months post-op, which is the current standard of care. No additional x-rays will be obtained.

A secondary outcome measure will be the incidence of dysphonia, as measured by the Voice Handicap Index (VHI-10), as well as other validated outcome measures (NDI, VAS, EQ-5D). The questionnaires will take approximately 20 minutes to complete and will be administered in the hospital, during the post-operative clinic visits with the surgeon, or over the phone. The surgeons will also listen to the patient's voice at these different time points and comment on dysphonia as being absent, mild, moderate, or severe.

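### The plan asks whether IV or local steroid is the better route, but the two steroid arms also use different drugs, so the trial can rank two regimens and cannot credit a difference to route

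*Combined protocol and SAP*

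**What the plan says.** The question is put in terms of route throughout. Objective 2 (Section 2.0) is "If steroids are useful, determine which method of steroid administration is most efficacious (IV versus local application"; its parenthesis makes clear that method means route. The hypothesis in the same section reads, in part, "local application of steroids in ACDF surgery will lead to a decreased incidence of dysphagia, in the postoperative period as compared to intravenous steroids", with control as the other comparator. The Synopsis objective is "Local application of steroids in ACDF surgery will lead to decreased incidence of dysphagia compared to intravenous steroids or a control group". The Title and Short Title also set local steroid against intravenous steroid without naming an agent. Section 1.0 describes the evidence gap in equally general terms, saying there is "no current spine literature that directly compares the efficacy of intravenous steroids versus local steroids" for dysphagia or dysphonia.

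The arms are more specific. In Section 5.0, group II receives "10 mg of intraoperative intravenous decadron with gel foam sponge placed on cervical plate" and group III receives "40mg of triamcinolone on gel foam sponge dabbed on the anterior cervical plate". The Synopsis gives the same drugs and doses. Nothing in the protocol or its statistical plan explains why different agents were chosen, states a dose equivalence between them, or limits the conclusion to these two regimens.

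**The concern.** A reader of Objective 2 expects an answer of the form *local is better than IV*, or the reverse. Between groups II and III the drug changes whenever the route changes. If group III has less dysphagia, the cause could be local delivery, triamcinolone at 40 mg, or both. If the groups look alike, a real route effect could be hidden by an opposing drug effect.

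What is at stake is the conclusion. Section 5.0 notes that there is no standard of care and that IV or local steroid use is left to the surgeon. A finding worded by route could therefore be carried over to any IV or local steroid, which these arms cannot support even if the trial runs exactly as planned.

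**Working it through.** The plan states no figure on this point, so there is none to reproduce. The power of 0.92 in Section 6.0 concerns detecting a difference in EAT-10 score, not what would explain one. The check is to set the arms against the question.

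**Step 1. Inputs (Section 5.0; drug and dose also in the Synopsis).**

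| | Group II | Group III |
|---|---|---|
| Drug and dose | decadron 10 mg | triamcinolone 40 mg |
| Route | intravenous | local, at the plate |
| Gel foam sponge on plate | yes | yes |

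The sponge is matched. Drug (with its dose) and route are not. Dose is kept with the drug because milligrams of two different agents are not comparable as a separate feature.

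**Step 2. Drug by route.**

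| | Intravenous | Local |
|---|---|---|
| Decadron 10 mg | group II | no arm |
| Triamcinolone 40 mg | no arm | group III |

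Only the diagonal is filled. To isolate route, at least one row would need both cells; to isolate drug, at least one column would.

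**Step 3. What the contrast estimates.** Take the simplest case, in which drug and route effects add. Let *r* be the effect of changing from IV to local with the drug held fixed, and *d* the effect of changing from decadron 10 mg to triamcinolone 40 mg with the route held fixed. Then

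(mean of group III) − (mean of group II) = Δ = *r* + *d*.

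This is one equation in two unknowns. The same Δ is obtained with *r* = Δ and *d* = 0 (all route), with *r* = 0 and *d* = Δ (all drug), or with any other pair that sums to Δ. If Δ = 0, then *r* = −*d*, which allows a route effect of any size offset by the drug. Allowing drug and route to interact adds a further unknown and no further equation.

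**Step 4. Does sample size help?** No. More patients estimate Δ more precisely, but *r* and *d* enter only through their sum. The same holds if the outcome is the incidence of dysphagia rather than a mean score.

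**Step 5. Does anything in the documents fix *d*?** Setting *d* = 0 would need a statement that the two drugs at these doses are equivalent. None is given, and none is supplied here from outside sources.

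**The case against.** The strongest reply is that nothing is concealed. The Synopsis states drug and dose for both steroid arms close to its objective, and Section 5.0 repeats them, so the route terms can be read as shorthand for the defined arms. Where practice is left to the surgeon, comparing one IV strategy with one local strategy is a legitimate pragmatic question. No test, estimate or enrolment decision changes, Objective 1 does not depend on route, and any harm arises only if a later report overstates the result.

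Much of this stands. The randomized comparison is sound and the issue is one of interpretation. But disclosing the arms does not narrow the claim. Objective 2 asks about method, defines it by route, and no other sentence limits the answer to these regimens. The objective is where the later report will take its wording, so the limit belongs there.

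Three stronger readings are tempting and should not be drawn:

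- *The comparisons with control are also confounded, by the sponge.* Section 5.0 says only "Subjects would be randomized to group I (control group, no steroid" and does not mention a sponge for that group. Silence is weak evidence here, because the Synopsis omits the sponge for groups II and III although Section 5.0 gives it to both. Whether controls receive one is an open question, not a demonstrated fault.
- *Dose is a further, independent confounder.* Once the drug differs, its dose is part of that difference. Giving one drug by both routes would still require the doses to be justified, since systemic and local exposure differ.
- *The background evidence shows a mismatch.* Section 1.0 cites IV methylprednisolone, which neither arm uses. That has no bearing on whether group II versus group III separates route from drug.

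**Conclusion.** The point holds as a limit on what may be concluded. Group II versus group III is a valid randomized comparison of 10 mg intravenous decadron with 40 mg local triamcinolone, each with a sponge on the plate. It cannot show that a difference, or its absence, is due to route, so Objective 2 as worded cannot be answered by this design.

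The size is best described as complete aliasing: no drug is given by both routes, so the data contain no information on the split. How large a misattribution could be cannot be stated, because the documents give no figure for the drug effect. A reader might infer that the trial or its randomization is invalid; the documents do not support that.

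The conclusion rests on two assumptions: that the arms are delivered as Section 5.0 describes them, and that method in Objective 2 means route, as its own parenthesis indicates. The wording should be corrected, but the defect does not call for a redesign.

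**What to change.** 1. **Objective 2.** Reword along these lines: *Should steroids prove useful, determine which of two regimens works better: decadron 10 mg given intravenously during surgery together with a gel foam sponge on the plate, or triamcinolone 40 mg carried on a gel foam sponge at the plate.*
2. **Hypothesis and Synopsis objective.** Use the same two descriptions wherever local is set against IV.
3. **Title and Short Title.** Name the two regimens, or keep the wording and add a qualifier in the Synopsis that the terms refer to these regimens. Otherwise the most visible route-only statement remains.
4. **Section 2.0.** Add one sentence: *The trial compares these regimens and does not separate route from drug and dose.*

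Arms, sample size, endpoints and tests are unchanged. The cost is a few lines of text and a narrower claim. If the sponsor wants an answer about route itself, at least one drug would have to be given by both routes with justified doses. That would be a different trial and is not needed to correct this plan.

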3.0 SELECTION OF SUBJECTS

3.1 INCLUSION CRITERIA:

- All patients undergoing ACDF (single or multi-level) for the treatment of cervical radiculopathy or myelopathy with Drs. [name], [name], and [name].
- All subjects must have given signed, informed consent prior to registration on study.

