Additionally, a chart review will be performed from 1/1/2013 to 12/30/2016 from NMH Medical records (PRIMES, Cerner PowerChart) and NMFF Medical Records (EpicCare, IDX/GE Centricity) to obtain the following data: Complications such as infection, post-operative hematoma, airway compromise, and recurrent laryngeal nerve palsy. All data collected from chart review will be de-identified and noted on the Data Collection Form. Each subject will be assigned a study number and all data will be linked to that number using the Coded Identifier List. The PI will identify which charts will be reviewed. The chart review will be performed by the PI, co-investigators, or authorized study coordinator.

There are potential physical risks from being in this study. The use of steroids may have an adverse effect on wound healing and/or transiently elevate blood sugar. There have been no documented wound complications from using either IV or local steroids in the setting of ACDF. Furthermore, we purposely excluded patients with a history of diabetes or other endocrine disorder in an attempt to minimize this potential side-effect or complication. Another possible risk related with participation in this study is the loss of privacy. To reduce these risks, all of the information collected will be de-identified and stored in a password protected file on a password protected computer. Additionally, some of the questions asked in the surveys may be upsetting, or the subject may feel uncomfortable answering them. If the subject does not wish to answer a question, they may skip it and go to the next question.

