6.0 STATISTICAL PLAN

We will use T score or ANOVA to compare EAT-10 scores, VHI scores, and EQ-5D, and Chi square for subjective findings. The P value will be set at 0.05.

A power analysis was performed to determine the sample size needed. Based on previous studies evaluating the EAT-10 in normal patients and those with dysphasia the analysis concluded: with total sample size 85 (Group I: 25, Group II: 25, Group III: 25) and estimated standard deviation of EAT-10 as 12.7, **power = 0.92**

Drs. [name], [name], and [name], perform approximately 6 ACDFs a month. This would allow us to collect our proposed sample size in approximately 12-14 months.

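### Single- and multi-level ACDF are both eligible, but the plan has no pre-specified way to detect or adjust for a chance imbalance in levels between arms of 25

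*Combined protocol and SAP*

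**What the plan says.** Section 3.1 makes eligible "All patients undergoing ACDF (single or multi-level) for the treatment of cervical radiculopathy or myelopathy", with no cap or quota on levels; the Synopsis says the same.

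Section 5.0 describes one allocation pool: "The 75 envelopes will then be shuffled to create a random assortment". Assignment follows by a draw: "The circulating nurse in the OR will at random choose one envelop prior to the start of the operative procedure". No strata are mentioned.

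The chart review in section 5.0 is "to obtain the following data: Complications such as infection, post-operative hematoma, airway compromise, and recurrent laryngeal nerve palsy". The Data Collection Form in the Appendices has columns for those four complications and the subject number. The Coded Identifier Form holds identifiers only.

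The analysis in section 6.0 is "We will use T score or ANOVA to compare EAT-10 scores, VHI scores, and EQ-5D, and Chi square for subjective findings". It names no covariate, stratum or subgroup. Planned size is given as "with total sample size 85 (Group I: 25, Group II: 25, Group III: 25"). Those arm sizes sum to 75, so the working below uses 25 per arm.

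**The concern.** The number of levels sets the extent of the anterior exposure, so it could plausibly influence swallowing after surgery. The protocol treats the distinction as worth naming in its eligibility rule, then drops it.

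Simple shuffling with 25 per arm can leave the arms visibly different on such a factor. If levels are prognostic, part of the observed difference between arms then reflects case mix rather than steroid use. Even with balanced arms, an unadjusted test leaves explainable variation in the error term. Section 2.0 needs several contrasts (steroid v none, IV v local, local v control), so an imbalance between any two arms matters.

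If a reader of the results asks whether the arms were comparable on levels, the plan as written provides no answer. An adjustment chosen after the data have been seen carries much less weight than one fixed beforehand.

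**Working it through.** **The plan's own figure.** Section 6.0 states power of 0.92 with "estimated standard deviation of EAT-10 as 12.7" and 25 per group. No EAT-10 difference is given, so the power cannot be reproduced, only back-solved. For two arms, two-sided 0.05, normal approximation: (1.960 + 1.405) × 12.7 × √(2/25) = 3.365 × 3.592 = 12.1 points. That figure says nothing about levels. Only the SD and the arm size are used below.

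**Inputs**
- Arm size 25, three arms (sections 5.0 and 6.0).
- EAT-10 SD 12.7 (section 6.0), taken as the total within-arm SD.
- Multi-level share: not in the documents. Assumed at 30% and 50%; 70% mirrors 30%.
- Effect of multi-level surgery: not in the documents. Assumed as 60% v 30% incidence, or 2, 4 or 6 EAT-10 points.

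**Step 1: chance of imbalance.** Fix M multi-level patients among 75. Under a random split into three arms of 25, the probability of counts a, b, c (summing to M) is C(25,a) × C(25,b) × C(25,c) / C(75,M). Sum this over the splits that show the stated gap. Five patients of 25 is 20 points; seven is 28 points.

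| Multi-level patients | Given pair, gap ≥ 5 | Some pair, gap ≥ 5 | Some pair, gap ≥ 7 |
|---|---|---|---|
| 38 (about 50%) | 0.21 | 0.40 | 0.16 |
| 22 (about 30%) | 0.16 | 0.34 | 0.11 |

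Treating the arm counts as independent binomials gives nearly the same: 0.20 and 0.41 for a gap of at least 5 at a 50% share, and 0.16 and 0.34 at 30%.

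**Step 2: shift in the comparison from a 20-point imbalance.** Shift = imbalance × level effect.
- Incidence: 0.20 × (0.60 − 0.30) = 0.06. At a 50:50 mix, average incidence is 0.45, so SE = √(2 × 0.45 × 0.55 / 25) = 0.141, and 0.06 / 0.141 = 0.43 SE.
- EAT-10: SE = 12.7 × √(2/25) = 3.59. The shifts are 0.20 × 2 = 0.4, 0.20 × 4 = 0.8 and 0.20 × 6 = 1.2 points, that is 0.11, 0.22 and 0.33 SE.

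**Step 3: variance that adjustment could remove** (share of outcome variance due to levels at a 50:50 mix).
- Incidence: 0.25 × 0.30² / (0.45 × 0.55) = 0.0225 / 0.2475 = 9.1%.
- EAT-10: 0.25 × 2² / 12.7² = 0.6%; 0.25 × 4² / 12.7² = 2.5%; 0.25 × 6² / 12.7² = 5.6%.

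An imbalance of this size is therefore quite likely somewhere among the three arms, but its effect on the estimate is modest, below half a standard error under every assumption tried.

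**The case against.** A reader might infer that the result would be biased. The documents do not support that. Under random allocation, a chance imbalance does not bias the estimator on average, and the ordinary standard error already allows for it. What remains is confounding in the one sample realised, plus lost precision.

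A reader might also infer that an imbalance could never be corrected. That goes too far. The Coded Identifier Form links subjects to record numbers, section 5.0 provides for chart review and routine x-rays, and section 7.0 keeps identifiable data until a year after completion. Levels could probably be recovered. Recovery is not assured by the plan, because the record systems named in section 5.0 are those of NMH and NMFF while the title pages list other sites, but it is far from impossible.

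Nor does the missing column on the Data Collection Form prove that levels go unrecorded. That form also lacks columns for treatment arm and for every questionnaire, although section 5.0 clearly collects the questionnaires. It is not the full case record. The plan is silent on recording levels, and that is all it shows.

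Two further objections stand in part. No section says that dysphagia depends on levels, so every size above is conditional. Site, surgeon and preoperative EAT-10 are unadjusted too; the last is already collected under section 5.0 and is an obvious covariate. The documents give no ground for ranking levels above these. This argues for adding levels to a short list of covariates, not for leaving them out.

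**Conclusion.** The point holds as a gap in pre-specification. Eligibility mixes single- and multi-level surgery, and the plan neither stratifies on levels, nor lists them for collection, nor includes them in the analysis.

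If 30 to 50% of patients are multi-level, the probability is about one in three to two in five that some pair of arms differs by 20 points or more. If levels are prognostic to the assumed degree, such a gap moves the comparison by about 0.1 to 0.4 SE, and leaving levels out forgoes roughly 1 to 9% of outcome variance. Both the multi-level share and the level effects are assumptions. If levels do not predict dysphagia, neither consequence arises. The case for change rests on its low cost and on making the realised comparison interpretable, not on a threat to the validity of the randomization.

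**What to change.** 1. Record the number of levels for every subject at every site, as planned before the envelope is opened, so that the covariate precedes randomization. This assumes the planned number is settled by then, which the documents do not state.
2. Report levels by arm in the baseline table.
3. In section 6.0, pre-specify single v multi-level as a factor in the primary comparison: ANCOVA for EAT-10, and a level-stratified test or logistic model for incidence. If enrolment has begun, this can still be done, provided it is fixed before outcomes are examined by arm.

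The cost is one form field and one degree of freedom.

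Stratifying the envelopes by level is optional. Four sites are listed, and section 4.0 has each collaborating site recruit its own subjects. The plan does not say who holds the envelopes. If each site held its own, two strata would mean 4 × 2 = 8 sets for 75 patients. Small fixed blocks should be avoided: only subjects are stated to be blinded, and consent may be taken in the pre-operative hold area, so staff who know past assignments could predict later ones.
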